11.0 Statistical/Data Analysis Plan

11.1 Statistical Considerations:

List the statistical methods to be used to address the primary and secondary objectives, specific aims, and/or research hypotheses. Explain how missing data and outliers will be handled in the analysis. The analysis plan should be consistent with the study objectives. Include any sub-group analyses (e.g., gender or age group). Specify statistical methods and variables for each analysis. Describe how confounding variables will be controlled in the data analysis

The primary outcome variable for this research study binary (successfully stop the pulse: yes/no) and we conducted a power analysis for a parallel group non-inferiority trial. Assuming the two arms have the same high successful rate, with 80% power, and define the non-inferiority limit as 10% (so that a difference bigger than this would matter in practice), we estimated sample size required for each group is 13 applications (at least), so a total sample size of 26 applications (at least). Given the potential missing data and to ensure we will have enough statistical power for the final analyses, we will set the total sample size of 40 applications for this study. Since the tourniquet will be applied to participants' both legs (not at the same time), each leg will be one application and one participant will be able to fulfill two applications. As such, we will recruit no more than 20 participants for the study session and one additional participant for the training session.

11.2 Sample Size:

A total of 21 participants will be recruited. We will recruit no more than 20 participants that allow us to complete 40 applications, with 20 applications in each arm. We will recruit one additional participant for the training session.

11.3 Total number of subjects requested (including records and specimens):

21

11.4 If you are recruiting by study arm, please identify the arms of the study and how many subjects will be enrolled in each arm

We will recruit no more than 10 participants (20 applications) for each study arm.

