The procedures will then be repeated to a participant's other leg for the other arm. For example, if a participant is initially assigned to the CAT and uses the right leg for tourniquet application. The participant will then be in the SMART TQ arm for the left leg.

Termination Procedures

For the first tourniquet application on each leg, the observer will use doppler ultrasound to assess the participant's foot for a present or absent dorsalis pedis pulse. The observer will make the assessment at the location previously marked with a surgical marker. As soon as the pulse is determined to be present or absent, the observer will verbally tell the medical professional, "remove the tourniquet now."

For the second tourniquet application on each leg, the medical professional will tighten the tourniquet on top of the neonatal blood pressure cuff as described. The study team member will record the pressure. As soon as the pressure is noted, the study team member will tell the medical professional, "remove the tourniquet now."

Participant Post-study Assessment

Following the application of two tourniquets to both legs, the study team will ask the participant to rest while lying on the table for five minutes. After five minutes, the study team member will ask the participant the following questions:

- Do you have any persistent pain beyond mild aching at the application site?
- Do you have numbness, tingling, or other abnormal sensations?
- Does your leg feel weak?

If the answer is yes to any question, the team member will ask the participant to rest for five more minutes and re-ask the questions. If the answer to any question is still yes, the study team member will recommend that the participant seek medical care at an emergency department or with the participant's physician. If the study team member or participant is concerned that they are experiencing a medical emergency, they will call 9-1-1 and alert any of the medical professionals assisting with the study for assistance.

If the answer to the questions is no, the study team member will ask the participant to walk up and down the hall in the MDL. The study team member will observe the participant ambulating. If the person feels normal while walking, they can be discharged from the study.

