11.5 Please provide a justification for your sample size

The primary outcome variable for this research study binary (successfully stop the pulse: yes/no) and we conducted a power analysis for a parallel group non-inferiority trial. Assuming the two arms have the same high successful rate, with 80% power, and define the non-inferiority limit as 10% (so that a difference bigger than this would matter in practice), we estimated sample size required for each group is 13 applications (at least), so a total sample size of 26 applications (at least). Given the potential missing data and to ensure we will have enough statistical power for the final analyses, we will set the total sample size of 40 applications for this study. Since the tourniquet will be applied to participants' both legs (not at the same time), each leg will be one application and one participant will be able to fulfill two applications. As such, we will recruit no more than 20 participants for the study session and one additional participant for the training session.

11.6 Data Analysis Plan: Complete description: Background, Objectives, Design, Step by Step how the project is going to be done, Data analysis plan:

Given that the primary study outcome variable is binary, we will use a chi-square test for the analysis. Descriptive statistics will be used to describe other study variables, including participants' demographic information.

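### The claimed 80% power at a 10% limit does not hold: at a true one-sided error rate of 10% or less, even 20/20 versus 20/20 cannot exclude a 10% deficit

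*Combined protocol and SAP*

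**What the plan says.** The only objective (9.3) is to show that SMART TQ is non-inferior to CAT in occluding arterial flow. The primary outcome is binary: pulse stopped or not.

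Sections 11.1 and 11.5 give the same sample-size paragraph. It describes a parallel-group non-inferiority calculation: "Assuming the two arms have the same high successful rate, with 80% power", and "define the non-inferiority limit as 10" per cent. From this, "we estimated sample size required for each group is 13 applications (at least), so a total sample size of 26 applications (at least". To allow for missing data, "we will set the total sample size of 40 applications for this study", and 11.2 speaks of enrolling numbers "that allow us to complete 40 applications, with 20 applications in each arm". The success rate is described only as high. Alpha, sidedness, formula and interval method are not given.

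Section 10.1 has the procedure repeated on the participant's "other leg for the other arm", so the comparison is within participant. Section 11.6 names one primary analysis: "we will use a chi-square test for the analysis".

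**The concern.** A non-inferiority claim needs a test that could reject a 10-point deficit. With very high success rates and 13 or 20 applications per arm there are almost no failures to count. The question is then whether the best possible data would be enough.

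This is the situation to expect. Under 10.1 the operator hears the doppler and tightens until the signal stops, which pushes success towards 100% in both arms. If both arms succeed 99% of the time, the chance of no failure in 40 legs is 0.99^40 = 66.9%. If that result cannot meet the limit, the trial's most likely outcome cannot support its only claim. A non-significant chi-square, or a clean sheet, might then be reported as non-inferiority when neither shows it.

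**Working it through.** **Inputs.** From 11.1 and 11.5: limit 0.10, power 80%, equal success rates, 13 per arm stated, 20 per arm planned. Assumed because not stated: a common success rate p near or below 100%, and one-sided alpha of 2.5%, 5% or 10%.

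**1. Reproducing the 13.** The normal-approximation formula is n = 2p(1-p)(z_alpha + z_beta)² / 0.10².

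- p = 0.99, one-sided 5%: 2 × 0.99 × 0.01 × (1.645 + 0.842)² / 0.01 = 12.24, rounded up to 13.
- p = 0.992, one-sided 2.5%: 12.46, rounded up to 13.
- p = 0.986, one-sided 10%: 12.45, rounded up to 13.

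So 13 requires p of about 0.989 to 0.990 (5%), about 0.992 (2.5%) or 0.985 to 0.987 (10%). At one-sided 5% the same formula gives 25 for p = 0.98, 59 for 0.95 and 112 for 0.90. Expected failures per arm of 13 are 13 × 0.008 = 0.10, 13 × 0.01 = 0.13 and 13 × 0.014 = 0.18, far too few for a normal approximation.

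**2. What a perfect result can show.** Put the truth exactly at the limit: CAT 100%, SMART TQ 90%. Every CAT application succeeds, so a perfect table has probability 0.9^n: 0.254 at n = 13 and 0.122 at n = 20. A rule that accepts a perfect table has at least that false-positive rate. With CAT always succeeding, each pair depends only on the SMART TQ leg, so the same figure applies to 20 pairs.

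**3. Lower limits for a perfect result, one-sided 95%.** The score limit is -z²/(n + z²), for two groups and for pairs (Tango). The exact limit is -(1 - 0.05^(1/n)).

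- n = 20: -2.706/22.706 = -11.9% (score); -13.9% (exact).
- n = 13: -2.706/15.706 = -17.2% (score); -20.6% (exact).

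The score statistic against a 10% deficit is 0.10/√(0.09/n): 1.49 at n = 20 and 1.20 at n = 13. Both are below 1.645.

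**4. Power, by enumerating both binomials (Farrington-Manning score test).**

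| Success in both arms | 13 per arm, one-sided 5% | 20 per arm, one-sided 5% | 20 per arm, one-sided 2.5% |
|---|---|---|---|
| 100% | 0% | 0% | 0% |
| 99% | 0.6% | 15% | 1% |
| 98% | 2% | 22% | 4% |
| 95% | 8% | 26% | 10% |

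The 15% can be seen by hand. The main accepted table is SMART TQ 20/20 with CAT at 19/20 or fewer: 0.99^20 × (1 - 0.99^20) = 0.818 × 0.182 = 0.149. At n = 20 the maximum over success rates of 85% to 100% is 26.4% at one-sided 5% and 12.6% at 2.5%. The paired Tango test peaks at 26.9% and 12.6% (success of 90% or more, non-negative within-person correlation).

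**5. The chi-square in 11.6.** It is undefined on a perfect table. Without continuity correction, against CAT 20/20, SMART TQ 17/20 gives p = 0.072 and 16/20 gives p = 0.035. With true rates of 100% and 90%, the chance of three or fewer SMART TQ failures in 20 is 0.867. So a device at the limit avoids significance 86.7% of the time (this includes the 12.2% with a perfect table, where no test can be computed).

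**The case against.** The 13 is not a slip of arithmetic. Under the Wald rule that matches the formula, enumerated power at 99% success and one-sided 5% is 87.8% with 13 per arm and 82.1% with 20, so for that rule the 80% claim is true. That stands as an account of where the figure came from, but it does not rescue the claim. The Wald interval has zero width on a perfect table and so accepts it automatically. With CAT at 100% and SMART TQ at 90%, its error rate is 25.4% at n = 13 and 12.2% at n = 20.

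Alpha is unstated and might have been lenient. At nominal one-sided 10% the score test does accept 20/20 versus 20/20, with power of 82% at 99% success and 76% at 98.6%. Its true size is 12.2%, and at n = 13 its power at 98.6% is only 14%. The conclusion must therefore name the error rate.

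The 12.2% is a worst case. For 99% versus 89%, a perfect table has probability (0.99 × 0.89)^20 = 8.0%; for 98% versus 88%, 5.2%. Both still exceed 5%. The benchmark score test is itself slightly liberal (5.4% at nominal 5%, n = 20), which if anything flatters the power figures.

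The chi-square figures assume no continuity correction, and 11.6 does not say which version is meant. With the correction, 17/20 gives p = 0.23 and 15/20 gives p = 0.056, so up to five failures escape. That makes the plan worse.

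Finally, 11.4 counts 10 participants and 20 applications for each arm, which could be read as both legs in one arm. Section 10.1 supports pairing by leg, but the two need reconciling before a paired method is fixed.

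**Conclusion.** The concern holds. The fault is a large-sample formula used where it fails, with its inputs undisclosed. At one-sided 5%, 20 applications per arm give 0% power at 100% success, about 15% at 99% and at most about 27% for success rates of 90% or more. At one-sided 2.5% the ceiling is about 13%. A perfect result excludes only deficits larger than about 12% (score) or 14% (exact). The ruling-out of a perfect table rests on control of the error rate at the worst case of 100% versus 90%, and it holds for one-sided 2.5%, 5% and 10%. It does not depend on which success rate the plan assumed. The power figures rest on the assumed rates and alphas shown. Missing applications would lower the information further. Because non-inferiority is the sole objective, and 11.6 contains no test of the limit, this must be corrected.

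**What to change.** In 11.1 and 11.5, state the success rate and alpha that gave 13, and withdraw the claim that 13 or 20 applications per arm provide 80% power at 10%. Suggested replacement:

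> With 20 pairs and no failures, only deficits larger than about 12% (score) or 14% (exact) are excluded (one-sided 95%). With the score limit, power to exclude 10% at one-sided 5% is 0% at 100% success and at most about 27% for success rates of 90% or more.

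If the exact limit is chosen, compute its own power and state that instead.

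In 11.6, replace the chi-square as primary analysis with the difference SMART TQ minus CAT and one pre-named lower limit suited to paired legs (Tango score or exact), with its alpha. Claim non-inferiority at 10% only if that limit lies above -10%; otherwise report the deficit that was excluded. State that neither a non-significant chi-square nor a perfect table is sufficient. If a nominal one-sided 10% score limit is used, disclose its true size of 12.2%. Reconcile 11.4 with the leg-by-leg allocation in 10.1.

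No added enrolment is requested. For reference, a perfect result meets the 10% limit at a true one-sided 5% only from 29 pairs (0.9^29 = 0.047), at 10% from 22 and at 2.5% from 36. These are not adequate sample sizes: the two-sample score test needs about 42 per arm for 80% power at 98% to 99% success and one-sided 5%.

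The cost is rewording 11.1, 11.5 and 11.6, plus clarifying 11.4. The downside is a much less favourable stated power, and a perfect result could not be reported as non-inferior at 10%.

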In January 2020, the research team conducted a pilot study to evaluate this novel layperson tourniquet in a community lay public sample recruited from at the NBC Health Expo in Washington, DC. Findings of this pilot study were promising. One highlight of the results was that the proportion of participants who applied the tourniquet correctly using the layperson tourniquet was significantly higher than that using the CAT (93.3% versus 6.3%). Moreover, for when asked about their favoritism toward the tourniquet, 93.3% favored the novel layperson tourniquet, whereas 68.8% favored the CAT.

In addition to research results, feedback provided by the participants in this pilot study allowed the research team and the manufacturing partner to make adjustments and improvements to the testing device. Now we have completed a pilot study evaluating overall user experience of the novel layperson tourniquet, our next step is to conduct a functionality study examining the function of this novel layperson tourniquet and to see if it performs on par with the CAT.

9.3 Objectives/Specific Aims/Research Questions:

Describe the purpose and objective(s) of the study, specific aims, and/or research questions /hypotheses

The objective of the study is to determine if the novel layperson tourniquet (SMART TQ)'s ability to occlude arterial blood flow is non-inferior to a Combat Application Tourniquet (CAT).

9.4 Study Design:

Describe study design in one to two sentences (e.g., prospective, use of existing records/data /specimens, observational, cross-sectional, interventional, randomized, placebo-controlled, cohort, etc.). Specify the phase – Phase I, II, III, or IV – for FDA-regulated investigational drug research

This study will be a single blinded, randomized clinical trial.

9.5 Target Population:

Describe the population to whom the study findings will be generalized

The study will benefit the general public.

9.6 Benefit to the DoD:

State how this study will impact or be of benefit to the Department of Defense

Research findings and information collected from this research study would help ongoing efforts of developing a layperson tourniquet.

10.0

Study Procedures, Data Management, and Privacy

10.1 Study Procedures:

Describe step-by-step how the study will be conducted from beginning to end

This study will be a single blinded, randomized clinical trial. The study will be conducted in a room at USU's Multidisciplinary Laboratories.

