The study has two arms: SMART TQ is the experimental arm and CAT is the control arm..

The study will consist of three groups of individuals:

- **Medical professionals who apply the tourniquet (we will call this group, medical professionals in this protocol). Each medical profession will be assigned to a study arm and switch to the other study arm halfway to reduce practice effects and minimize biases. They will be identified via the research team's professional network.**
- **Volunteers who offer their legs for tourniquet application (we will call this group of individuals study participants).**
- **Blinded observers who will use a doppler to check and monitor pulse. Absence of the dorsalis pedis pulse will be used to indicate occlusion of blood flow. The pulse monitored by the blinded observers will be used as an outcome for this research study. The only person blinded in the study will be the person checking for a successful application by measuring the doppler pulse – that is the blinded observers. There will be a bedsheet, or similar screen, placed between the portion of the participant's leg that has the tourniquet applied and the participant's foot where the doppler pulse will be**

measured. In addition, the research team will provide blinded observers noise-canceling headphones to minimize the influence of audio instructions provided by the SMART TQ.

We will recruit two medical professionals and two blinded observers and consent volunteers (i.e., participants). The detailed information for the informed consent process is summarized in the later section.

Training Session

Two medical professionals will attend a training session prior to the study. The session will allow the study team to verify that medical professionals can apply both types of tourniquets successfully. We anticipate this training session lasting no more than one hour and will recruit one participant for the training session.

Study Session

Upon the completion of the informed consent, participants will be assigned study ID numbers and then randomly assigned to a study arm: SMART TQ or CAT. The study steps are below:

- A study participant enters the study room, completing a demographic information sheet and taking blood pressure, and then lies down with the face and torso facing up.

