- To capture the baseline dorsalis pedis (DP) pulse: A blinded observer uses a doppler ultrasound to check DP pulse, the artery pulse on the surface of the foot. Doppler ultrasound is a small medical ultrasound machine that uses high-frequency sound waves to measure the amount of blood flow through the arteries and veins. The doppler ultrasound probe will be placed on the exposed foot, a pulse detected, and the location where the pulse is detected on that foot will be marked with an "X" using a surgical marker, and the doppler probed removed. This marked location will be where the doppler probe is placed later to determine whether there is a pulse.
- The research team member will measure the circumference of the leg at the area of tourniquet application. To keep the application location consistent across all the participants, we will mark where on the leg the tourniquet should be placed for each application.
- A medical professional records which leg will be used for tourniquet application (left leg or right leg)
- The medical professional applies the tourniquet. This is the first application of the tourniquet. *For tourniquet application, in order to signal medical professional stops tourniquet application (i.e., stops tightening the tourniquet), the doppler signals will be audible to medical professionals. Once the doppler signals stop, the medical professionals will stop applying/tightening the tourniquet.*
- Upon the completion of the tourniquet application, the blinded observer records the presence or absence of a dopplerable pulse. A blinded observer again uses a doppler ultrasound probe to check the dorsalis pedis (DP) pulse, the artery pulse on the surface of the foot, at the previously marked "X" location on the foot.
- The medical professional removes the tourniquet and the study participant takes a break.
- The medical professional places a blood pressure cuff first and then places a tourniquet over the blood pressure cuff. This is the second application of the tourniquet. The blood pressure cuff will be attached to a fluid (e.g., water)

pressure sensor to measure surface pressure under the tourniquet. The medical professional will tighten the tourniquet until the doppler pulse is eliminated. The medical professional will then read and record the pressure readings.

- **The medical professional removes the tourniquet.**

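### The trial produces 20 within-person pairs, but it is sized as parallel groups and analysed with an unspecified chi-square test that cannot test the 10% non-inferiority limit

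*Combined protocol and SAP*

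**What the plan says.** The objective in section 9.3 is to show that SMART TQ is non-inferior to CAT in occluding arterial flow. Sections 11.1 and 11.5 set the non-inferiority limit at 10%.

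On the design, section 10.1 has each participant "then randomly assigned to a study arm: SMART TQ or CAT", and then: "The procedures will then be repeated to a participant's other leg for the other arm". Its worked example puts CAT on the right leg and SMART TQ on the left leg of the same person. For the leg, it says only that the medical professional records which one is used. Section 11.2 agrees with this layout: up to 20 participants "that allow us to complete 40 applications, with 20 applications in each arm".

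The other statistical sections read differently:

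- 11.1 and 11.5: "we conducted a power analysis for a parallel group non-inferiority trial", giving at least 13 applications per group at 80% power with equal, high success rates. Neither the success rate nor alpha is given.
- 11.4: "We will recruit no more than 10 participants (20 applications) for each study arm".
- 11.6: "we will use a chi-square test for the analysis". No pairing, margin, confidence interval or significance level is given.

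**The concern.** Section 10.1 describes a within-person comparison, and the statistical sections describe two independent groups. A reader cannot tell from the plan which analysis will be run. Pearson's test and McNemar's test are both chi-square tests, although the parallel-group wording points to the unpaired one.

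The more serious issue is the hypothesis. Both tests ask whether the two success rates are equal, while the objective asks whether SMART TQ is worse by less than 10 points. A non-significant test of equality in a small trial could be reported as showing that the devices are equivalent. If every application succeeds, which is the result the planning assumption makes most likely, the named test returns nothing. The 80% power claim has also not been shown for any analysis that fits the design and the limit.

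A smaller gap is that the arm is randomised but the plan does not say that the allocation of device to leg is random.

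**Working it through.** **1. Design count.** 20 participants x 2 legs = 40 applications. With one device per leg, each arm has 20 applications from all 20 participants. The figure in 11.4 (10 participants x 2 legs = 20 applications) works literally only if both legs of a person get the same device, which 10.1 excludes.

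**2. Reproducing the 13 per group.** For independent groups, n = 2p(1-p)(z_a + z_b)^2 / 0.10^2. The documents give neither p nor alpha, so both are assumptions here.

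- p = 0.99, one-sided 0.05: 0.0198 x (1.645 + 0.842)^2 / 0.01 = 12.24, rounded up to 13.
- p = 0.99, one-sided 0.025: 15.54, rounded up to 16. To get 13 at this level, p must be about 0.992.
- At one-sided 0.05, p = 0.98 gives 25 and p = 0.95 gives 59.

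The stated figure therefore implies a success rate near 0.99.

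**3. Effect of ignoring the pairing.** With within-person correlation rho, the ratio of unpaired to paired standard error is 1/sqrt(1-rho): 1.00, 1.12, 1.41 and 2.24 at rho = 0, 0.2, 0.5 and 0.8. In 20 actual pairs the two Wald standard errors can differ only if both arms have at least one failure. That probability is 1 - (2p^20 - p11^20), with p11 = p^2 + rho p(1-p). Over rho 0-0.8 it is 3-15% at p = 0.99, 11-28% at 0.98 and 41-58% at 0.95. For example, 1 against 0 failures gives 0.0487 either way; 2 against 1 failures with one shared gives 0.0829 unpaired and 0.0487 paired.

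**4. What the chi-square test can show.**

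- 17/20 against 20/20: Pearson statistic = 40 x (20 x 3)^2 / (20 x 20 x 37 x 3) = 3.24, p = 0.072. The deficit of 15 points is beyond the limit, yet the result is not significant.
- 20/20 in both arms: the expected number of failures is 0, so Pearson is undefined. McNemar, (b-c)^2/(b+c), is 0/0. The probability of this outcome is p11^20: 67-79% at p = 0.99 and 13-29% at p = 0.95.

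**5. Testing the limit with 20 pairs.** With no discordant pairs the Tango lower limit is -z^2/(n + z^2).

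- One-sided 0.05: -2.706/22.706 = -11.9%.
- One-sided 0.025: -3.841/23.841 = -16.1%.

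Enumerating every table of 20 pairs shows that no tied or worse result for SMART TQ clears -10% at either level. One CAT-only failure with no SMART-only failure gives -7.5% (0.05) or -11.9% (0.025).

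**6. Exact multinomial power of the Tango rule, 20 pairs, equal true rates.**

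| p | One-sided alpha | rho 0 | 0.2 | 0.5 | 0.8 |
|---|---|---|---|---|---|
| 0.99 | 0.05 | 14.9% | 12.6% | 8.6% | 3.7% |
| 0.99 | 0.025 | 1.4% | 0.9% | 0.4% | 0.1% |
| 0.95 | 0.05 | 26.7% | 26.9% | 24.4% | 14.5% |
| 0.95 | 0.025 | 10.4% | 8.8% | 5.2% | 1.3% |

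**7. Pairs needed for a perfect tie to clear -10%.** At 0.05, 24 pairs give -10.13% and 25 give -9.77%. At 0.025, 34 give -10.15% and 35 give -9.89%.

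**The case against.** The strongest reply is that pairing is a side issue. With positive correlation an unpaired analysis is conservative, so it loses precision but does not inflate false claims of non-inferiority. Near 100% success the two analyses usually coincide, and the large standard-error ratios need a correlation that the documents do not supply. All of this stands. Nor does pairing cause the low power: at 20/20 against 20/20 the unpaired score limit is the same. The weight of the point therefore rests on the untested limit.

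Section 11.4 may also be loose wording for 10 people starting on each device, since it answers a form prompt about enrolment by arm. That reading is plausible, but it is not what the sentence says, and the sentence still has to be reconciled with 10.1 and 11.2. The silence on leg allocation is a gap, not a contradiction.

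The Tango interval is one choice among several, and the power figures depend on it and on assumed inputs. That is true, but it shows why the method must be named beforehand: a Wald interval has zero width at a perfect tie and would pass automatically, whereas a score interval fails.

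Finally, 10.1 has each medical professional assigned to one arm and switching halfway. If followed, a participant's two legs may be treated by different operators, which a plain paired interval does not address.

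**Conclusion.** The concern holds and should be fixed. The documents describe 20 within-person pairs, size a parallel-group trial, and name a test that cannot answer the non-inferiority objective. The contradiction and the missing test of the limit rest on the text alone.

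The size of the problem rests on assumptions: true success of 0.95-0.99, within-person correlation of 0-0.8, one-sided alpha of 0.05 or 0.025, and a score interval. On that basis a perfect tie misses the 10% limit, SMART TQ must be observed to do better than CAT to pass, and power is about 4-27% (0.05) or 0.1-10% (0.025) instead of 80%. The pairing mismatch itself costs only precision, and little of it at the success rate implied by the plan's own calculation.

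**What to change.** - **11.6:** replace the chi-square test with the paired difference in success proportions (SMART TQ minus CAT) and a paired score (Tango) confidence interval. Compare its lower limit with -10% at a stated one-sided alpha, and report the concordant and discordant pair counts.
- **11.1 and 11.5:** describe the design as paired within participant. Restate the sample size and power for that method, giving alpha, the assumed success rate and the assumed discordance.
- **11.4:** say that there are 20 participants, each contributing one SMART TQ leg and one CAT leg, with 20 applications per arm.
- **10.1:** state that both device order and allocation of device to leg are randomised, and record the operator for each leg.
- **Disclosure:** state that 20/20 in both arms gives -11.9% (0.05) or -16.1% (0.025), so a tied result cannot show non-inferiority with 20 pairs.

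The cost is wording in five sections, leg allocation in the randomisation list, and a much less favourable power statement. No extra enrolment is needed if the limitation is stated. If the sponsor wants a perfect tie to pass, at least 25 pairs (0.05) or 35 pairs (0.025) are needed, which is 5 or 15 more participants than the cap of 20 and means amending 11.2 and 11.3. Those numbers do not guarantee 80% power: at p = 0.95 and rho 0-0.8, exact power is 43-79% with 25 pairs (0.05) and 37-73% with 35 pairs (0.025).
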